Section 13.3: Visit 3 (Day 42): Procedures and data recorded from visit 3 (Day 42) Bullet 4	Confirm of continued eligibility prior to reinfusion of radiolabeled cells (record current health status, current medications, negative RBC bacterial testing and/ or visual inspection, donor viral screen, hemolysis <1% of stored LR-RBC)	Confirm of continued eligibility prior to reinfusion of radiolabeled cells (record current health status, current medications, negative RBC bacterial testing and/ or visual inspection, donor viral screen, hemolysis ≤1% of stored LR-RBC)	

DOCUMENT REVISION HISTORY

SYNOPSIS	
Sponsor:	Terumo Blood and Cell Technologies
Study Title:	An In Vivo 24-Hour Recovery Study of Leukoreduced RBCs After Automated Separation of Whole Blood by the Reveos System and Storage for 42 Days
Study Number:	CTS-5085
Device Description:	The Reveos® Automated Blood Processing System (Reveos system) is an automated whole blood processing system, not cleared for use in the United States. The Reveos System has been available outside the United States since 2012 and is seeking United States Food and Drug Administration (FDA) 510(k) clearance as an automated whole blood processor. The Reveos System is an integrated manufacturing system that processes whole blood (WB) units into blood components and designed to minimize manual blood processing variables resulting from processing time, product and procedural variability. The Reveos System consists of the primary device (equipment) that uses centrifugal force to separate whole blood into its components, a disposable blood bag set to collect and store separated components, and a software program to manage the operations. The Reveos disposable blood bag set contains CPD (citrate phosphate dextrose) anticoagulant, additive solution formula 5 (AS-5), and a red blood cell (RBC) leukoreduction filter. The Reveos System can simultaneously process up to 4 whole blood units into 4 RBC units, 4 leukoreduced plasma units, and 4 interim platelet units (IPU). The CPD/AS-5
	RBC product is leukoreduced and may be stored up to 42 days.
Intended Use:	 Intended Use of the Reveos Device The Reveos device is intended to automatically separate units of whole blood into blood components. Intended Use and Description of the Reveos Blood Bag Set The Reveos Blood Bag Set is intended to collect a unit of whole blood and to process the unit on the Reveos device, producing blood components. Intended Use of the Reveos System Manager Software
	The Reveos System Manager is a software application that manages Reveos procedures and processing data.
Objectives:	The primary objective of this study is to evaluate whether the LR-RBCs derived from whole blood and processed with the Reveos System meet FDA criteria for 24-hour recovery after 42-day storage.
Primary Endpoint:	The primary endpoint is the 24-hour in vivo RBC recovery after 42-day storage.

Page 8/59

Reveos Automated Blood Processing System
Clinical Investigation Plan: CTS-5085

Study Design:	This is a prospective, open-label, multicenter study to evaluate whole blood derived red blood cells processed using the Reveos System.		
	The main objective is autologous in-vivo recovery of radiolabeled leukoreduced RBCs derived from whole blood processed using the Reveos System and stored for 42 days		
	DAY -14- 0		
	Screening for all participants.		
	DAY 0		
	One (1) unit of whole blood (500mL +/- 10%) will be collected, and the whole blood unit will be processed with the Reveos System within 8 hours. The whole blood will be separated into three blood components: red blood cells, plasma and platelets. RBCs will be leukoreduced with red blood cell (RBC) leukoreduction filter integrated into the Reveos Blood Bag Set.		
	RBC mass recovery and leukoreduction post filtration will be measured.		
	LR-RBC units will be stored at 1-6°C for 42 days. Plasma and platelet products will be discarded per site policy.		
	DAY 42:		
	Stored RBCs will be tested for hemolysis, in addition visual inspection and /or bacterial testing, and donor viral screens will be confirmed negative.		
	Radiolabeling: An aliquot of 42-day stored autologous LR-RBCs will be radiolabeled with chromium-51 (⁵¹ Cr). An aliquot of freshly collected and prepared RBCs will be radiolabeled with technetium-99m (^{99m} Tc). The labeled aliquots will then be combined and infused to the autologous donor. Blood samples will be collected approximately at 5, 7.5, 10, 12.5, 15, 20, and 30 minutes post infusion.		
~ ~ ~	Blood sample for 24-nour RBC recovery will be drawn. This visit concludes the study.		
Study Sites Planned:	Hoxworth Blood Center, Cincinnati, OH and Bloodworks Northwest, Seattle, WA		
Study Duration:	Approximately 57 days per participant		
Target Population:	Healthy adult participant		
Number of Subjects Planned:	24 evaluable participants (up to 50 enrolled).		
Inclusion Criteria:	1. Healthy volunteers., of either gender		
	2. Age 18 years or older.		
	3. Normal health status as per AABB criteria for healthy donor.		
	4. Able to commit to the study schedule.		
	5. Meets the inclusion criteria defined by the Blood Center for whole blood donor. These criteria are based on FDA Regulations and AABB standards. Note: Participants who are deferred from volunteer community donations because of travel restrictions, piercings, tattoos or other reasons by PI approval may participate in the study, as products are re-transfused to the autologous donor.		
	6. Participants of childbearing potential (either male or female) must agree to use medically acceptable method of contraception throughout of the study.		
	7. Females of childbearing potential must be willing to take a pregnancy test prior to WB donation and infusion of radiolabeled RBCs.		
	8. Signed and dated informed consent form.		
Exclusion Criteria:	1. Pregnant or nursing females.		
	2. Serum ferritin <12 ng/mL		
	3. Has previously completed this study with evaluable data points.		

Reveos Automated Blood Processing System
Clinical Investigation Plan: CTS-5085

	4. Participation currently, or within the past 30 days, in another investigational trial that would potentially interfere with the analysis of this investigation (eg, pharmaceutical).		
	5. As determined by the Investigator		
	a. Has been diagnosed with a blood disorder(s) affecting RBC characteristics (eg, G-6PD).		
	 Reported history of RBC autoantibodies/autoimmune hemolytic anemia, RBC alloantibodies. 		
	c. Clinically significant acute or chronic disease		
	 Reported history of known hypersensitivity to technetium or chromium. 		
	e. Treatment with any medication as specified in site deferral list (based on AABB medication deferral list for blood donors).		
	6. Other unspecified reasons that, in the opinion of the investigator make the subject unsuitable for enrollment.		
Statistical Methodology:	Based on FDA criteria for in vivo RBC quality, the following criteria will be assessed:		
nictiouology.	The mean 24-hour, post-transfusion, in vivo red cell recovery of at least 75% with a standard deviation of $\leq 9\%$, and the lower limit of a one-sided 95% confidence interval for the population proportion of successes is $\geq 70\%$ where an individual success is defined to be a recovery of at least 75%. If there are no more than 3 failures (ie, 3 recoveries <75%), in an N of 24 or no more than 2 failures in an N of 20, than the lower limit of a 95% one-sided will be at least 70%.		

Cr-51	Sodium Chromate 51
СТА	Clinical Trial Agreement
CTS-5085	Protocol Number
DMC	Data Monitoring Committee
EC	Ethics Committee
EDC	Electronic Data Capture
FDA	US Food and Drug Administration
G-6PD	Glucose 6 Phosphate Dehydrogenase Deficiency
GCP	Good Clinical Practice
Hgb	Hemoglobin
Het	Hematocrit
IB	Investigator's Brochure
ICF	Informed Consent Form
ICH	Helsinki, International Conference of Harmonization
ICSH	International Committee for Standardization in Hematology
IDE	Investigational Device Exemption
IPU	Interim Platelet Unit
IRB	Institutional Review Board
ISO	International Organization for Standardization
LTFU	Lost to Follow-up
MDR	EU Medical Device Regulation
mL	Milliliter
MOP	Manual of Procedures
ng	Nanogram(s)
PE	Procedure Emergent

PEAE	Treatment Emergent Adverse Event
PI	Principal Investigator
PVC	Polyvinyl Chloride
RBC	Red Blood Cell
LR	Leukoreduced Red Blood Cell
SAE	Serious Adverse Event
SD	Standard Deviation
SOP	Standard Operating Procedure
Tc-99m	Technetium-99m pertechnetate
TMF	Trial Master File
UADE	Unanticipated Adverse Device Effect
US	United States
USID	Unique Study Identification Number
WB	Whole Blood

1 STATEMENT OF COMPLIANCE

This study will be conducted according to this Clinical Investigation Plan (CIP), Good Clinical Practice (GCP) as described in the International Council for Harmonization Guidance for Industry E6(R2), and, as applicable, United States Code of Federal Regulations (CFR) concerning clinical studies (45 CFR Part 46; 21 CFR Parts 50, 56, 312 and 812), International Organization for Standardization (ISO) 14155:2020, European Union Medical Device Regulation (EU MDR) 2017/745, and other regulatory requirements of the region(s) where the study is conducted. The study will not begin until the required approvals or favorable opinions from the Ethics Committee (EC) and regulatory authority have been obtained, as applicable. As directed, any additional requirements imposed by the EC or regulatory authority will be followed. All individuals responsible for the design and conduct of this trial have completed Human Subjects Protection Training. Any applicable information required per above regulations that is not contained in this CIP may be submitted in separate documentation and will be attached to the CIP as an appendix. All essential documents will be archived together in the Trial Master File (TMF).

2 INTRODUCTION

Terumo Blood and Cell Technologies is a corporation that continuously develops medical devices for blood manufacturing and cell therapies. These devices include products for whole blood (WB) collection and processing, apheresis, therapeutic apheresis, pathogen reduction, and cell expansion. The focus in this study is whole blood processing with the Reveos® Automated Blood Processing System (Reveos System).

Blood transfusions have been widely used in medical practice since the early 20th century.¹ Blood transfusion is the most common procedure during hospital stays in the United States.² In 2017 over 12 million WB and apheresis red blood cell (RBC) units were collected in the US and approximately 85% of these units were WB collections.³ Patients may receive a unit of WB or individual blood components to treat any particular condition and the Global Database on Blood Safety reports that in high income countries 97% of WB donations are processed into blood components.⁴

Whole blood consists of blood components with cellular elements, colloids, and crystalloids. Having different relative densities, sedimentation rate, and size, blood components can be separated when centrifugal force is applied. This separation is controlled in part by the specific gravities of these components including, in increasing order, plasma, platelets, leukocytes, and RBCs.⁵ WB units are currently separated into RBC, plasma, and platelet components through a labor intensive, largely manual processes, often including multiple steps. The first fully automated system for WB unit processing developed by Terumo Blood and Cell Technologies was Atreus (BK080010), which could process one unit of WB into blood components in one run.⁶

The Reveos System can process up to four (4) WB units in one run. It combines balancing, centrifugation, component separation, and sealing into one platform.

As an automated blood processor, the Reveos System is beneficial in reducing manual blood processing drawbacks including processing time, and variability in the procedures and end product leading to standardized blood component yield and quality.

The aim of this study is to evaluate the in-vivo 24-hour recovery of autologous RBCs produced with the Reveos System and stored for 42 days, in order to meet the FDA's criteria for manufactured RBCs.

3 DEVICE DESCRIPTION

The Reveos® Automated Blood Processing System is an automated WB processing system. Within the protocol it will be referred as Reveos System. The Reveos System has been released for sale in certain regions accepting the CE mark since 2013, Terumo Blood and Cell

Technologies is seeking US Food and Drug Administration (FDA) 510(k) clearance of the Reveos System as an automated whole blood processor.

The Reveos System consists of the Reveos device (processing equipment) that uses centrifugal force to separate WB into its components, a disposable Reveos blood bag set intended to collect and store separated components, and a software program to manage the operations.

Reveos Device

The Reveos System (Figure 3-1) is an easy-to-use platform that automates and integrates the manual steps involved in WB processing. The system processes up to 4 units of WB to produce RBCs, leukoreduced plasma, platelets, and residual leukocytes with a single centrifugation step. The Reveos System (Figure 3-2) consists of a computer-controlled centrifuge equipped with a rotor with 4 fixed buckets, in which the Reveos blood bag set can be placed. Each bucket contains a hydraulic-driven expressor to press the different fractions of the centrifuged blood from the top to the satellite bags.

- 1 Device lid 2 Power switch
- 3 Stop button
- 4 Touch screen
- 5 Barcode scanner
- 6 Access drawer
- 7 Casters

Figure 3-2 Reveos Device Rotor Compartment

- 1 Bucket
- 2 Bucket lid
- 3 Bucket-lid latch4 Blood component bag
- holder
- 5 Valves and line sensors
- 6 Hydraulic bladder
- 7 Centrifuge basin
- 8 Bucket sensors
- 9 Rotor

The Reveos System produces three components from each unit of whole blood processed: a plasma unit, an RBC unit, and an interim platelet unit (IPU) Interim Platelet Unit (IPU). The IPU is pooled with other IPUs to create a therapeutic platelet dose. A residual leukocytes unit is also produced as a by-product. All buckets must contain a loaded blood bag set or counterbalance bag before beginning a procedure.

Reveos System Manager

Reveos System Manager is a software application that manages procedures and product data. This data is automatically transferred from the Reveos device to the Reveos System Manager. The Reveos System Manager lets users perform the following tasks:

- Configure Reveos devices
- Define users and assign permissions
- Configure barcodes and procedures
- Record and output process and product data
- Track information entered into the Reveos System Manager
- Standardization of workflows
- Report generation

Reveos Blood Bag Set

The Reveos blood bag set (Figure 3-3) consists of medical grade Polyvinyl Chloride (PVC) container closures (i.e. blood component bags and tubing). The blood bag set is steam sterilized, single use disposable set consisting of a needle connected to a sampling bag and a WB collection bag used to collect and process 500 mL $\pm 10\%$ WB. The WB bag has 70 ml of anticoagulant (CPD-citrate phosphate dextrose), and the RBC component bag has 111 mL of additive solution formula AS-5 (Optisol), and an integrated RBC leukoreduction filter.

A general overview of the investigational Reveos blood bag set with: 1) WB bag (processing bag) containing CPD anticoagulant, 2) Platelet bag, 3) Plasma bag, 4) RBC bag containing red cell additive solution (AS-5), 5) Residual leukocyte bag, 6) Cryoprecipitate bag 7) Blood collection assembly (needle, needle injury protector, sample/diversion bag) 8) RBC leukoreduction filter.

The Reveos System primary equipment (processing device) does not come into contact with the study participants. After Reveos System processing, RBC units are diluted with AS-5 additive solution and transferred through an integrated leukoreduction filter to the RBC bag for storage.

CPD and AS-5

(Optisol) solutions used in the disposable sets were approved for use with TERUFLEX (or IMUFLEX) blood bag Systems in 1988 (NDA: BN880217).

Citrate Phosphate Dextrose (CPD) (Table 3-1)

The WB bag has 70 ml of anticoagulant CPD.

Table 3-1	The composition of CPD	

CPD Solution			
Description	Concentration (1000ml)	Reveos Blood Bag Set (70ml)	
Dextrose Anhydrous	23.2 g	1.624 g	
Sodium Citrate	26.3 g	1.841 g	
Citric Acid	3.27 g	0.229 g	
Sodium Dihydrogen Phosphate			
Dihydrate	2.51 g	0.176 g	
Water for Injection	977 ml	up to 70 ml	

Additive solution, AS-5 (Table 3-2)

The RBC component bag has 111 mL of additive solution formula AS-5.

AS-5 Solution			
Description	Concentration (1000ml)	Reveos Blood Bag Set (111ml)	
Dextrose Anhydrous	8.18 g	0.908 g	
Sodium Chloride	8.77 g	0.973 g	
Mannitol	5.25 g	0.583 g	
Adenine	0.315 g	0.035 g	
Water for Injection	984 ml	up to 110 ml	

Table 3-2The composition of AS-5

Relevant research personnel will be trained on the use of the Reveos System. Device accountability will be tracked throughout the study.

The investigational products will be labeled per 812.5 (a) *"Caution- Investigational Device. Limited by Federal (or United States) law to investigational use."*

4 INTENDED USE STATEMENT

Intended Use of the Reveos Device

The Reveos device is intended to automatically separate units of whole blood into blood components.

Intended Use and Description of the Reveos Blood Bag Set

The Reveos Blood Bag Set is intended to collect a unit of whole blood and to process the unit on the Reveos device, producing blood components.

Intended Use of the Reveos System Manager Software

The Reveos System Manager is a software application that manages Reveos procedures and processing data.

5 NONCLINICAL STUDIES

Nonclinical studies for verification and validation are ongoing for the Reveos System.

To date a feasibility, in vitro study for Reveos System processed RBCs has been done. The study evaluated hemolysis on Reveos System processed and LR RBC units (n=52). The units were stored in CPD/AS-5 for 42 days. The mean hemolysis \pm SD was 0.18% \pm 0.09% with range of 0.08% - 0.55%, meeting FDA defined criteria for hemolysis.

6 CLINICAL TRIAL EXPERIENCE

The investigational Reveos System intended for US market does not have clinical trial experience.

7 **RATIONALE FOR THE CURRENT STUDY**

Terumo Blood and Cell Technologies is seeking 510(k) clearance from FDA/CBER for the Reveos® Automated Blood Processing System (Reveos System).

The proposed study will provide validation on the in vivo performance of LR-RBC units derived from WB processed with the Reveos System. The results will provide data as to whether the Reveos System produced LR-RBC can maintain required levels of 24-hour in vivo recovery that meet FDA criteria for RBC.⁷

8 **OBJECTIVES**

8.1 **Primary Objective**

The primary objective of this study is to evaluate whether the LR-RBC derived from WB processed with the Reveos System meet FDA criteria for in vivo 24-hour recovery.

Based on FDA criteria for in vivo RBC quality, the following criteria will be assessed:

LR-RBC mean 24-hour recovery $\ge 75\%$ with SD $\le 9\%$ and one-sided lower confidence limit for population proportion of RBC in vivo recovery 70%[†]. Success is >75%.

†Allows for low recoveries (<75%) in 2/20 or 3/24 volunteers.

If all three criteria are met, the Reveos System will be deemed to have met the FDA criteria for 24-hour in vivo RBC recovery.

Performance criteria will be evaluated in healthy adult participants, who receive radiolabeled, autologous infusions of LR-RBC components after being stored for 42 days at 1-6°C.

9 ENDPOINTS

9.1 **Primary Endpoint**

The primary endpoint is the 24-hour in vivo RBC recovery.

LR-RBC mean 24-hour recovery \geq 75% with SD \leq 9% and one-sided lower confidence limit for population proportion of RBC in vivo recovery 70%[†]. Success is >75%.

†Allows for low recoveries (<75%) in 2/20 or 3/24 volunteers.

10 INVESTIGATIONAL PLAN

10.1 Study Design

Prospective:

- Evaluation of LR- RBC recovery
- Healthy adult volunteers
- 24 total evaluable participants enrolled (i.e., approximately 12 participants at each site)
- Single arm autologus reinfusion of radiolabelled RBCs
- Double radiolabel with ⁵¹Cr (LR-RBCs for recovery) and ^{99m}Tc (Fresh RBCs for RBC volume/mass determination)

Multi- Center:

- Hoxworth Blood Center
- Bloodworks Northwest

This study evaluates Day 42 RBC recovery. After donation and processing of WB with the Reveos System, the RBCs are leukoreduced (LR) and stored for 42 days. An autologous aliquot of stored LR-RBCs and fresh RBCs will be radiolabeled with ⁵¹Cr and ^{99m}Tc, respectively, and reinfused to the donor. RBC recovery testing will be performed at 24-hour post-infusion.

All procedures related to labeling, infusion, sampling and recovery/mass determination will follow site common standardized procedures and standard operating procedures (SOPs).

The procedures for radiolabeling of RBCs to evaluate RBC recovery are based and adapted from methods recommended by International Committee of Standardization in Haematology (ICSH) *Recommended Methods for Radioisotope Red-Cell Survival Studies* 1980⁸ and previously published literature by Moroff and colleagues *Proposed Standardization of Methods for Determining the 24-Hour Survival of Stored Red Cells,* 1984⁹. The method of calculating the blood volume with ^{99m}Tc is based on the ICSH *Recommended Methods for measurement of Red-Cell And Plasma Volume* 1980¹⁰.

10.2 Study Duration

The total study duration is expected to last 6 months from first participant enrollment. Each study participant will have a total of 4 study visits (Figure 10-1) including screening within a time span of 57 days (1.9 months). Visit details are described in section 13.

- Study visit 1(Screening 0-14 days)
- Study visits 2 to 4 (over approximately 43 days)

Figure 10-1 Study Flow

11 STUDY POPULATION

11.1 Number of Participants and Selection

It is estimated that up to 50 volunteers will be enrolled to allow targeted twenty-four (24) evaluable recovery endpoints. Healthy adult volunteer study participants will be enrolled at two (2) centers; approximately 12 at each study center. Study participants will come from the general population. Eligible WB donors exhibiting normal health status and vital signs as determined by standard American Association of Blood Banks (AABB) blood donation criteria.

Volunteers who cannot commit to completing all study requirements should not be considered for enrollment. No medical records are accessed during inclusion exclusion determination, all medical history is based on known or self-reported history of the prospective participants. A participant can screen multiple times but participate only once for the study. The Informed Consent process described below will be undertaken following determination of initial eligibility.

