11.3 Exclusion Criteria

Exclusion criteria for participant selection:

- 1. Pregnant or nursing females.
- 2. Serum ferritin <12 ng/mL
- 3. Has previously completed this study with evaluable data points.
- 4. Participation currently, or within the past 30 days, in another investigational trial that would potentially interfere with the analysis of this investigation (eg, pharmaceutical).
- 5. As determined by the Investigator
 - a. Has been diagnosed with a blood disorder(s) affecting RBC characteristics (eg, G-6PD).
 - b. Reported history of RBC autoantibodies/autoimmune hemolytic anemia, RBC alloantibodies.
 - c. Clinically significant acute or chronic disease
 - d. Reported history of known hypersensitivity to technetium or chromium.
 - e. Treatment with any medication as specified in site deferral list (based on AABB medication deferral list for blood donors).
- 6. Other unspecified reasons that, in the opinion of the investigator make the subject unsuitable for enrollment.

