There is a possibility of bacterial overgrowth if bacteria have inadvertently entered the blood bag collection system. The stored LR-RBCs will undergo bacterial testing and/or visual inspection, per site's SOP. The results from this testing or inspection will be reviewed prior to the infusion of cells. Any participant with positive results will not be re-infused with their RBC. Total volume of blood drawn from subjects completing the study will be approximately 670 mL over 57 days. The standard blood center eligibility criteria for donating blood products includes tracking RBC loss. A standard single unit WB collection (211 ml of RBC loss) is between 450-550 mL. After a WB collection the body replaces the plasma in about 24 hours, RBCs are restored in two to four weeks, and platelets are replenished in about 72 hours.

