# 2.3 Study Populations

The Full Analysis Population will include all participants enrolled in the study and who met the eligibility criteria. Efforts will be made to obtain complete recovery data from all participants.

The Safety Analysis Population will include all participants enrolled in the study who met the eligibility criteria and were exposed to Reveos Blood Bag Set. The Safety Analysis Population will be utilized to assess safety of the device and procedure. It is possible for a volunteer to be included in the Safety Analysis Population more than once if they do not have an evaluable

Confidential Document

Doc No.: TMP-BS-01 Rev No.: 4.0

Revision No. 1.0

Document Date: 28-Apr-2022

Page 11 of 17

recovery endpoint. If this occurs, it will be noted in the relevant tables in the Clinical Investigation Report (CIR) though they will continue to be analyzed as separate participants.

The Evaluable Analysis Population will include participants who completed all study visits per protocol with a valid 24-hour recovery endpoint. The Evaluable Analysis Population will be used in the analysis of the primary endpoint. While the criteria allow for 20 or 24 participants, analysis will be based on all participants meeting the criteria of the Evaluable Analysis Population.

Data will be excluded from the Evaluable Analysis Population in the following situations:

- 1. Incomplete or incorrect procedure that affects the primary endpoint due to:
  - a. Equipment failure or malfunction (eg, filter plugs)
  - b. Unanticipated processing failure
  - c. Results of primary endpoint tests are not available
- 2. Protocol deviations that affect the primary endpoint due to:
  - a. Failure to follow collection procedures outlined in the device Operator's Manual, Instructions for Use (IFU) (Package Insert), Manual of Procedure(s), and site SOPs
- 3. Product non-reinfusable due to:
  - a. Product does not pass quality check for reinfusion (residual WBC, LR-RBC mass recovery, visual inspection, hemolysis, bacterial growth)
- 4. Participant issues
  - a. Participant lost to follow-up or withdrawn from study
  - b. Other participant issues (eg, inadequate access, reaction, needle abort)

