# 2.5.2 Safety Analyses

All adverse events collected will be provided for the Full Analysis Population by MedDRA system organ class and preferred term. Adverse event summaries for the purposes of device safety assessments will be limited to procedure-emergent adverse events (PEAEs), defined as any AE that occurs upon or after the exposure to the Reveos Blood Bag Set. PEAE summaries will be provided for the Safety Analysis Population.

Confidential Document

Doc No.: TMP-BS-01 Rev No.: 4.0

Revision No. 1.0

Document Date: 28-Apr-2022

Page 13 of 17

Tables will describe the frequency and percentage of all PEAEs, serious PEAEs, adverse device effects (ADEs), and unanticipated ADEs (UADEs). Additional presentations will summarize PEAEs by maximum reported severity; maximum relatedness to device, procedure, and medical history (related, not related); and those leading to discontinuation/termination. Concomitant medications used to treat PEAEs will also be summarized.

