# 4. CHANGES FROM THE PROTOCOL

	Summary of Changes			
Rationale:	This revision history captures the updates from Version 3.0 / 01 March 2022 of the CIP to Version 1.0 / 28-APR-2022 of the SAP.			
	Significant changes include the following:			
	
 
Changes and clarification were made to the definitions of the analysis populations.
 
The sample size discussion was updated to accommodate over enrollment.
 
The methods discussed for generating confidence intervals is inconsistent in the CIP. A one-sided lower exact 95% confidence limit will be provided for the proportion of treatment successes. Confidence limits presented for continuous demographic and safety parameters will be based on the normal approximation.
 
Dual label method endpoint for 24-hour recovery will also be analyzed which include mean, standard deviation, median, minimum, maximum, proportion of successes, one-side 95% lower confidence limit.
 
Administrative changes, section numbering, typographical error corrections, and minor wording changes for clarity, to make consistent throughout the text, or to make tables consistent with text as a result of these changes have been made and will not be reflected in the table below. These changes did not result in changes to the conduct of the study, so no CIP Amendment was conducted.
 
			
Change	Language from the CIP	Language from the SAP		
Modification	19.3.1 Full Analysis Population	Section 2.3 Study Populations		
	The Full Analysis Population will include all participants enrolled in the trial.	The Full Analysis Population will include all participants enrolled in the study and who met the eligibility criteria. Efforts will be made to obtain complete recovery data from all participants.		

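### CIP 11.1 allows one participation per volunteer, but SAP 2.3 counts a returning volunteer as a new participant, so procedure-emergent adverse event percentages would be per participation, not per person

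*Protocol*

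**What the plan says.** Three places bear on whether a volunteer may go through the study twice.

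- CIP 11.1: "A participant can screen multiple times but participate only once for the study".
- CIP 11.3, exclusion 3 (repeated in the Synopsis), excludes a person who "Has previously completed this study with evaluable data points". It is silent on someone who donated but whose data proved non-evaluable.
- SAP 2.3: "It is possible for a volunteer to be included in the Safety Analysis Population more than once if they do not have an evaluable" recovery endpoint. Membership of that population requires exposure to the Reveos Blood Bag Set. Repeats are to be noted in the report tables, "though they will continue to be analyzed as separate participants".

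On reporting, SAP 2.5.2 says: "PEAE summaries will be provided for the Safety Analysis Population". The tables give frequencies and percentages, and also summarise PEAEs by maximum severity and maximum relatedness. SAP 2.1 describes the population size printed in each table as the number of subjects enrolled.

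SAP section 4 shows the new safety population beside the text of CIP 19.3.2. It does not mention CIP 11.1.

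The risk text describes a single pass. CIP 16.1 says: "Total volume of blood drawn from subjects completing the study will be approximately 670 mL over 57 days". Table 13-1 gives a total of approximately 678.5 mL.

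**The concern.** The CIP contrasts screening, which may be repeated, with participation, which may not. A volunteer who has donated into the bag set has gone well beyond screening. The SAP nevertheless provides for that volunteer to come back. Two sites reading the same documents could treat the same returning volunteer differently.

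The second consequence is in the safety tables. If a person appears twice, the denominator counts that person twice, and the numerator may as well. A reader would take a percentage of participants to mean a percentage of people. Maximum severity and maximum relatedness are normally one value per person; a returning volunteer would supply two. CIP 12.3 assigns a sequential identification number after consent, and no rule links a returning volunteer's two records, so a per-person count might be hard to recover later.

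**Working it through.** **Can re-entry happen?** CIP 10.2 gives 57 days per participant in a study expected to last 6 months (about 182 days): 182 / 57 = 3.2. A second pass fits.

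**The plan's own figure.** The documents state no PEAE rate and no expected number of re-entries. The figure that can be reproduced is the primary-endpoint limit in CIP Table 19-1. The one-sided exact 95% lower limit for x successes in n is the 5th percentile of Beta(x, n - x + 1). For 21/24 this is Beta(21, 4), giving 70.77%, as stated. For 20/24 it is Beta(20, 5), giving 65.82%, as stated.

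**Does re-entry change that rule?** No. SAP 2.3 permits repeat inclusion only without an evaluable endpoint, and exclusion 3 bars anyone who completed with one. Each person therefore gives at most one value to the Evaluable Analysis Population.

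**Effect on PEAE percentages.** Let E be participations in the Safety Analysis Population, k re-entries, a participations with a PEAE, and d distinct people with a PEAE. Then:

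- percentage as the SAP counts it = a / E
- percentage of people = d / (E - k)

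Assumptions for illustration: E = 50 (the enrolment ceiling, taking all as exposed), a = 5, and each returning volunteer returns once. The reported figure is 5/50 = 10.0% whatever k is. If all events are in different people, d = 5. If events recur in the same people as far as possible, d = 5 - min(k, 2), because five events contain at most two pairs.

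| k | People (50 - k) | Events all in different people | Events paired where possible |
|---|---|---|---|
| 0 | 50 | 5/50 = 10.0% | 5/50 = 10.0% |
| 1 | 49 | 5/49 = 10.2% | 4/49 = 8.2% |
| 2 | 48 | 5/48 = 10.4% | 3/48 = 6.25% |
| 3 | 47 | 5/47 = 10.6% | 3/47 = 6.4% |
| 6 | 44 | 5/44 = 11.4% | 3/44 = 6.8% |
| 10 | 40 | 5/40 = 12.5% | 3/40 = 7.5% |

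With fewer participations, E = 30 and k = 3, the reported figure is 5/30 = 16.7%, against 5/27 = 18.5% or 3/27 = 11.1% of people. The SAP figure can be too high or too low.

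**Single-pass risk text.** The Table 13-1 total is reached with the upper collection limit: 3.5 + 35 + 550 + 80 + 10 = 678.5 mL. Two complete passes would be 2 x 678.5 = 1,357 mL. This is an extreme, since many non-evaluable reasons (failed quality check, needle abort, withdrawal) can end a pass before infusion. A first pass that reached Day 42 and infusion would also mean a second isotope infusion.

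**The case against.** **Exclusion 3 is not permission.** It is one criterion among several, and a site must also obey 11.1. Read that way the CIP is coherent, and the SAP sentence is only a contingency for analysis. This stands in part: the CIP permits re-entry only by implication. But the SAP provides explicitly for an event that 11.1 forbids, and nothing says which governs. Reading participation as evaluable completion does not help, because CIP 12.3 starts a participant's involvement at consent.

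**Per-exposure counting suits a device, and repeats are disclosed.** Both are fair. The safety output is descriptive, with no test or success rule. But a note saying that repeats occurred does not give the per-person percentage.

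**Donor safeguards remain.** CIP 16.1 says donor eligibility includes tracking red-cell loss, and inclusion criterion 5 applies blood-centre donor criteria. The volume and isotope point is therefore a gap in the description, not evidence of an unprotected second donation.

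A reader might infer two stronger points that the documents do not support.

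- *That re-entry gives a failing volunteer a second chance at the 75% cut.* A move from 20/24 to 21/24 would first need a failing recovery to be ruled non-evaluable. That depends on the exclusions in CIP 19.4 and SAP 2.3 and the replacement rule in CIP 19.1 and SAP 2.2. A new volunteer filling the slot could produce the same swing.
- *That the SAP denies any change of conduct from re-entry.* The sentence "These changes did not result in changes to the conduct of the study, so no CIP Amendment was conducted" closes item 5, on administrative and typographical changes. The population definitions are item 1, listed separately as a significant change. The fair criticism is only that section 4 omits 11.1.

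**Conclusion.** The point holds in limited form. CIP 11.1 conflicts with SAP 2.3, exclusion 3 leaves the door open by implication, and no text reconciles them. As written, PEAE percentages equal per-person percentages only if nobody re-enters. In the assumed case of 5 PEAE participations among 50, a reported 10.0% corresponds to 6.25% to 12.5% of people for 1 to 10 re-entries. That range rests on assumed counts and one return per volunteer; the documents supply neither. Disposition and demographic summaries could carry the same double counting. The primary endpoint, its 21/24 rule and the 70.77% limit are unaffected. This should be corrected because it governs whom a site may accept and what the safety percentages mean, but it does not threaten the primary analysis.

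**What to change.** 1. State one re-entry rule, in the same terms, in CIP 11.1, exclusion 3 and SAP 2.3. List it against CIP 11.1 in SAP section 4.
2. If re-entry is kept, link a returning volunteer's records across identification numbers. Report PEAE numbers and percentages in SAP 2.5.2 per unique volunteer, each counted once per preferred term and once at maximum severity and maximum relatedness, with per-exposure counts alongside.
3. If re-entry is kept, reconcile the single-pass blood volume and isotope description in CIP 16.1 and Table 13-1 with the possibility of a second pass.

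The cost is a short CIP clarification, a few sentences in the SAP and one extra table column. If re-entry is dropped instead, some non-evaluable slots must be filled by new volunteers; the allowance of up to 50 enrolled for 24 evaluable leaves room for this.
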